#### 9.3 POPULATIONS FOR ANALYSES

All participants will be included in the analysis, including participants contributing only a partial data set. The only exception would be in cases where the PI, study statistician, and Exercise Physiology/Engineering/Radiology study Col-lead (for volume-load vs. lab-based vs. imaging-based data) agree there is legitimate threat to the validity of data collected in any individual participant due to technical error not identified at the time of assessment that cannot be resolved through post-processing (e.g., incorrect gain settings leading to signal saturation or failure of MRI field of view not covering the full extent of cervical musculature to be measured).

## 9.4 STATISTICAL ANALYSES

## 9.4.1 GENERAL APPROACH

Prior to the analysis, all data will be examined and transformed as necessary to achieve approximate normality. Descriptive statistics will be used to characterize the distribution, central tendency (mean, median), and variability (standard deviation, range, interquartile range) of each continuous variable. All subjects will be included in the analysis and an alpha of .05 will be considered significant for statistical testing.

## 9.4.2 ANALYSIS OF THE PRIMARY AND SECONDARY EFFICACY ENDPOINTS

We expect a percentage reduction in net head acceleration as the volume load of exercise performed increases over the 12 week exercise program, so we will assess net head acceleration on a logarithmic scale to allow us to model and detect a constant change. For example, a 20% reduction in net head acceleration corresponds to a difference of log(.8) on the log-scale, regardless of the initial value of net head acceleration. We will use linear mixed models to describe the longitudinal changes in log(net head acceleration) over the volume loads of exercise performed at each of the four study time points, and to test the significance of this change across the three exercise groups.

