## 4.3 JUSTIFICATION FOR DOSE

All subjects will exercise 2 days per week under the direct supervision of a study-assigned strength coach (National Strength and Conditioning Association Certified Strength and Conditioning Specialist, CSCS, certification), with a minimum of 1 day of rest between exercise sessions. Subjects will be assigned either to a high intensity neck strengthening exercise group or to a control exercise group performing only "shoulders-down" resistance exercises not directly targeting the neck. All exercises will be performed in accordance with National Strength and Conditioning Association standards. The neck strengthening program will include manual resistance exercises in sagittal-plane flexion and extension, coronal-plane lateral flexion to the left and right, and axial-plane rotation to the left and right, as well as dumbbell shoulder shrugs as previously described by our group. For each group, the exercise program

will progress in volume and intensity over the duration of the study, to accommodate muscular fitness adaptation. Such progression is considered vital to the long-term efficacy of resistance exercise programming.

The volume load of neck strengthening exercise will be calculated using a modified protocol previously employed by our group for the elbow flexors. For shoulder shrugs the volume load for each exercise session will be defined as the product of the dumbbell weight x the force of gravity (g= 9.8 m/s2) x the number of repetitions performed during the exercise session, to yield a volume load for the exercise session in N. During manual resistance exercise, the strength coach will hold a hand-held dynamometer against the subject's head to measure and record the force applied during manual resistance. For both dumbbell shrugs and manual resistance exercises, the total cumulative exercise volume load will be defined as the sum of the individual session volume loads over all exercise sessions completed by the subject. Since subjects assigned to the control group will not perform neck strengthening exercise, their exercise volume load will remain zero throughout the study.

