## 9.2 SAMPLE SIZE DETERMINATION

Our power calculation is based on AIM 1. Assuming net head acceleration (on the logarithmic scale) will follow linear trends over time, then our power calculation is based on comparison of the slope of this change, which has 9/14 of the variance, i.e., 36% less variance, than the underlying log(net head acceleration) measurements. As a result, the standardized effect size (Cohen's d value) of the slope is approximately 1.25 times greater than that of the underlying log(net head acceleration) measurements. Based on our own pilot data, we expect observed standardized effect sizes to be between .6 and 1.0 for log(net head acceleration), depending on the variability of the individual measurements across the 4 directions of motion. These values correspond with a 20% overall reduction in un-transformed net head acceleration. A total of 30 subjects in each exercise group (control and high intensity), will provide power of between .83 [for standardized effect size for log (net head acceleration) of .6 and 1.0 [for standardized effect size in the population. To account for the possibility of a drop-out rate of up to 20%, we will plan to enroll up to a total of 72 subjects.

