## 9.4.6 SUB-GROUP ANALYSES

We will include sex as a covariate in the statistical models, as well as explore possible interactions between sex and other independent variables, to identify any sex-based differences in the relationship between exercise volume load and the net head acceleration outcome.

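### Section 9.4.2 tests change over volume load while 9.2 powers a slope over time; read literally, the 9.4.2 test cannot be estimated, and its estimable load version is not randomised and, without a time term, credits shared decline to neck exercise

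*Combined protocol and SAP*

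**What the plan says.** The model for the primary and secondary endpoints is one sentence in 9.4.2. Linear mixed models will "describe the longitudinal changes in log(net head acceleration) over the volume loads of exercise performed at each of the four study time points" and "test the significance of this change across the three exercise groups". Only two arms remain in the current design (4.1, 4.3, 6.2).

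Section 4.3 defines cumulative load as the "sum of the individual session volume loads over all exercise sessions completed by the subject". For the comparator it says: "Since subjects assigned to the control group will not perform neck strengthening exercise, their exercise volume load will remain zero throughout the study".

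Other sections point in different directions:
- 9.1 states both hypotheses as a dose-response in volume load.
- 9.4.6 says "We will include sex as a covariate in the statistical models" and looks for "sex-based differences in the relationship between exercise volume load and the net head acceleration outcome".
- 9.2 assumes that the log outcome will "follow linear trends over time, then our power calculation is based on comparison of the slope of this change", a slope "which has 9/14 of the variance, i.e., 36% less variance, than the underlying log(net head acceleration) measurements".
- 1.1 and 3 define the endpoint as the value at Time Point 4.
- 4.2 says that the control arm is there to separate the effect of neck exercise from growth and general training.

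No section names a time term, a group-by-time term, random effects or a within-athlete covariance.

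**The concern.** The sentence in 9.4.2 can be read in three ways.

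- (a) A load slope in each arm, compared between arms. This is the literal reading, and the control slope does not exist.
- (b) One pooled load slope. This fits 9.1 and 9.4.6 and can be estimated. But load accrues from sessions attended and force achieved after randomisation, so its coefficient is not a randomised contrast. If no time term is added, it also absorbs any change common to both arms.
- (c) Slopes over time, compared between arms. This is the randomised comparison, and it is what 9.2 powers.

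The plan does not say which reading applies, so the analyst would choose after the data are in. Section 6.2 lists the study statistician among those not blinded. The choice governs both confirmatory endpoints, and 9.4.8 carries the same plan over to soccer heading. A shared decline is plausible: section 2.2 reports that head acceleration fell in both arms of the pilot.

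**Working it through.** **Inputs from the documents.** 30 per arm; four visits; standardised effect d = .6 to 1.0, equated with a 20% reduction; slope variance factor 9/14; power .83 and 1.0 (all 9.2); alpha .05 (9.4.1; two-sided assumed). Log-scale SD = |log .8|/d = .2231/.6 = .372, or .2231/1.0 = .223.

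**Assumed; the documents give neither.** Within-athlete correlation ρ with compound symmetry, and the size of any shared decline.

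**1. The plan's own figure.** Power = Φ(d·√(n/(2f)) − 1.96), where f is the variance of the three-step slope difference in units of 2·SD²/n. With f = 9/14, d = .6 and n = 30: .6 × √(15 × 14/9) = 2.898, and Φ(.938) = .826. At d = 1.0 it is .998. So .83 and 1.0 reproduce, for a slope over time 0, 1, 2, 3.

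**2. Estimability.** Load is zero whenever group = 0, so load × group equals load in every row. The design [1, load, group, load × group] has rank 3 of 4. Adding categorical time does not help: [1, visit, load, load × group] has rank 5 of 6. By contrast, [1, load], [1, load, group], [1, visit, load] and [1, group, time, group × time] all have full rank.

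**3. Share of a common decline credited to load.** Let both arms change by c·s, with s = (0, 1/3, 2/3, 1), no exercise effect, and intervention load equal to s. By generalised least squares, put
- v = 4/(1+3ρ)
- u = 2/(1+3ρ)
- w = Q/9, with Q = [14 − 36ρ/(1+3ρ)]/(1−ρ).

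For the model [1, load], share = (2vw − 2u²)/(2vw − u²). At ρ = .5: v = 1.6, u = .8, w = 1.511, so the share is (4.836 − 1.28)/(4.836 − .64) = .85.

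| ρ | 0 | .3 | .5 | .7 | .9 |
|---|---|---|---|---|---|
| load only | 53% | 75% | 85% | 92% | 98% |

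If load rises progressively (0, .2, .55, 1), the load-only share is 58–95%. With group added, the load slope is the intervention arm's own slope: 100% for linear load and at least 97% for progressive load. Sex is balanced by stratification and changes nothing. With time or visit in the model the share is 0%, because that term fits the shared decline exactly.

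**4. False-positive rate at ρ = .5, time omitted.** For load only, SE = SD × √[2v/((2vw − u²)·30)] = .159 SD. For load plus group, SE = SD × √(.9/30) = .173 SD. A total fall of 5% by Time Point 4 is log(.95) = −.0513. With load only and SD .372: .85 × .0513/.0593 = .73 standard errors, which rejects in .11 of trials.

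| Total shared fall | SD .372: load / load + group | SD .223: load / load + group |
|---|---|---|
| 5% | .11 / .13 | .23 / .26 |
| 10% | .32 / .37 | .71 / .78 |

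With no shared fall, or with time included and the covariance correctly specified, the rate is .05. A simulation with loads varying between athletes (1,000 trials per case, ρ = .5, load only) gives .12 and .25 for 5%, and .31 and .69 for 10%.

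**5. What 9.2 leaves unstated.** With a common baseline f = 9/Q, which equals 9/14 when Q = 14, at ρ = 0 or ρ = 11/21 = .524. With separate intercepts f = (9/5)(1−ρ), which equals 9/14 at ρ = 9/14 = .643. Power at d = .6:

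| ρ | .3 | .5 | .6 | .7 |
|---|---|---|---|---|
| common baseline | .76 | .82 | .87 | .93 |
| separate intercepts | .54 | .69 | .78 | .89 |

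**The case against.** The strongest reply is that 9.2 and 9.4.2 together already imply a comparison of slopes over time. Section 9.4.2 speaks of longitudinal change at four time points, 9.2 names the slope over time, and the stated power reproduces for that test. An aliased column would also show itself as soon as the model was fitted. This stands in part. A reader might infer that the primary analysis is impossible. The documents do not support that, because two of the three readings can be fitted. The fault lies in the specification, not in the data or the design. What remains is that 9.1, 9.4.2 and 9.4.6 all speak of volume load, and nothing says that 9.2 overrides them.

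A reader might also take .11–.78 as the plan's actual type I error. It is not. Those rates need the load reading, omission of time (which the plan neither writes nor excludes) and an assumed decline. The pilot had only 4 controls over 8 weeks, and section 2.2 gives no size for the fall.

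Nor does the arithmetic show that .83 is wrong. A common baseline reaches it at a moderate correlation of .524 and exceeds it at higher ones. Finally, one might suppose that the mixed model has a random intercept only and is anti-conservative for that reason. The plan names no such model, so this supports only a request to state the covariance.

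Which hypothesis is primary is the sponsor's scientific choice. A load model with time or visit in it is estimable and removes the shared-decline problem, though it remains non-randomised.

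**Conclusion.** The concern holds as a conflict between sections that needs correcting before analysis. The literal between-group test in 9.4.2 is not estimable. The load reading that best fits 9.1 and 9.4.6 is not a randomised comparison. With only the named terms it would credit between 53% and all of a shared decline to neck exercise, which defeats the purpose that 4.2 gives the control arm. The ranks follow from the documents alone. The shares rest on compound symmetry and a linear shared decline, and the error rates also on an assumed decline of 5% or 10% in total. The power in 9.2 is reproducible but incompletely documented: at d = .6 it runs from .54 to .93 over correlations .3 to .7, depending on baseline handling. The reference to three groups is left over from the removed arm and carries no weight.

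**What to change.** In 9.4.2, write: the primary test is the group-by-time coefficient (two-sided .05) in a two-group linear mixed model of log(net head acceleration) at visits 1–4, with time (0–3), group-by-time, sex and age category (the randomisation strata in 6.2). The model-based group difference at Time Point 4, three times the slope difference, is reported with its confidence interval.

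Also:
- State whether baseline means are common or separate by arm, and give a covariance structure that lets athletes differ in trend, such as random intercept and slope, or unstructured.
- Keep the volume-load dose-response analysis, always with time or visit in the model, and label it non-randomised. If the sponsor retains it as the primary hypothesis, adding that term is the minimum change.
- In 9.2, state the correlation and baseline handling behind 9/14 and .83, and restate power if the chosen model differs.
- Align 1.1, 3, 9.1 and 9.4.8 with the chosen contrast, and change three groups to two.

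The cost is wording and a little analysis work, with no new data. Dose-response would move to a supporting role unless the sponsor keeps it primary. The slope test relies on the linear trend already assumed in 9.2, and a categorical-visit sensitivity analysis would check it. Power may fall below or above .83 depending on the correlation.

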## 9.4.3 SAFETY ANALYSES

AEs and SAEs will be summarized by severity, relatedness, and expectedness using counts, with each AE counting only one time for a given participant, and will be presented in a table format.

# 9.4.4 BASELINE DESCRIPTIVE STATISTICS

Intervention groups will be compared on baseline characteristics (including demographics, cervical muscle attributes, and net head accelerations under each loading condition) to assess for the presence of any baseline differences between the groups before participation in the study-assigned exercise intervention. Categorical and continuous variables will be assessed using chi-square tables and ANOVA, respectively.

## 9.4.5 PLANNED INTERIM ANALYSES

Consistent with the original proposal submitted to and funded by NIH, a blinded interim analyses will be performed by the study statistician in Study Year 3, or upon protocol completion by 15 participants in the treatment group, whichever marker of the study mid-point comes first. The results of the interim analysis will be reviewed by the PI and shared with the study team for dissemination as preliminary study results, but will not be used to halt ongoing study activities.

In addition, the strength of the estimated total cervical muscle volume prediction algorithm with respect to MRI-based measured total cervical muscle volume will be reassessed by the study statistician on an ongoing basis throughout the study period. Pending determination of the strength of the estimated total cervical muscle prediction algorithm, the MRI portion of the study protocol will be amended to minimize the time and expense associated with MRI acquisition and analysis for the remainder of the study.

In the event that an immediate DSMB review is required in response to any AE(s), SAE(s), or UP(s) (see Sections 8.3.5-8.3.6 and 8.4.2), new study enrollment will temporarily be suspended until the DSMB has met and assessed the need for ongoing modification to study enrollment and/or study intervention activities. Ongoing study activities will continue without interruption unless an unexpected, study-related SAE occurs, in which case ongoing study activities associated with the portion of the study protocol deemed to have caused the SAE will be temporarily suspended pending DSMB review and recommendations.

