## 4 STUDY DESIGN

## 4.1 OVERALL DESIGN

In this single-site randomized clinical trial, 72 high school soccer athletes will complete a series of 4 laboratory assessment sessions before, during, and after a 12-week resistance training program including either high intensity neck strengthening exercises or control exercises not targeting the neck. During each laboratory assessment, measurements will be performed to assess key cervical muscle attributes, as well as the head's net acceleration under multiple loading conditions designed to reflect the range of impact scenarios encountered by athletes during sport participation. The primary loading conditions will be direct force application to the head using the customized loading apparatus designed by our group for our previous research and a standardized checking/blocking task involving impacts to the body with inertial force transmission to the head. In addition, a voluntary soccer heading task will be used as an exploratory loading condition.

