#### 6.2 MEASURES TO MINIMIZE BIAS: RANDOMIZATION AND BLINDING

Subjects will be randomized using a centralized electronic randomization tool with equal allocation to the control and high-intensity neck strengthening groups. Balanced block randomization will be used to ensure equal sex and age category balance between the groups. Age category will correspond to high school under-class (i.e., age 13.0 - 16.49 years at the time of randomization) vs. upper-class (i.e., age 16.50 – 19.99 years) status given the typical maturation occurring in adolescents through the high school years. Subjects will be considered enrolled in the trial upon randomization and available data will be included in the intention to treat analysis. The Study Statistician, Strength Coach, Study Coordinator, and PI (or his Co-I designee when necessary to make a determination of AE relatedness to the study) will not be blinded to subject group allocation. Other members of the study team, including those responsible for performing the laboratory- and radiology-based assessment will be blinded to group allocation status. Subjects will not be informed of their group allocation status, although they will be aware of whether or not they are performing neck strengthening exercises during their exercise sessions. Subjects will be instructed not to discuss whether they are performing neck strengthening exercises during their exercise sessions.

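### Does the undefined word blinded in Section 9.4.5 let interim results by arm reach the blinded assessors?

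*Combined protocol and SAP*

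**What the plan says.** Section 9.4.5 of the combined protocol and SAP says "a blinded interim analyses will be performed by the study statistician in Study Year 3". A second trigger can bring the analysis forward: "upon protocol completion by 15 participants in the treatment group, whichever marker of the study mid-point comes first". On release it says: "The results of the interim analysis will be reviewed by the PI and shared with the study team for dissemination as preliminary study results", and adds "but will not be used to halt ongoing study activities". It does not say which endpoints or contrasts are analysed, or whether the output is pooled, split by masked arm or split by named arm.

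Section 6.2 sets the blinding. The study statistician, strength coach, study coordinator and PI "will not be blinded to subject group allocation". For everyone else: "Other members of the study team, including those responsible for performing the laboratory- and radiology-based assessment will be blinded to group allocation status". Athletes are not told their group, but "they will be aware of whether or not they are performing neck strengthening exercises during their exercise sessions".

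Section 10.1.5 has the DSMB look once a year at safety and efficacy data for each arm.

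**The concern.** The analyst and the first reader both know the allocation, the word *blinded* is not defined, and the recipients include people who are meant to stay blinded. The output is also meant for dissemination, so it could travel beyond the team while athletes are still being tested.

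If results by arm were released, two groups might be influenced. Assessors might come to expect a certain result. Athletes, who know whether they train the neck, might change their effort, and the primary endpoint is measured while they brace. Section 4.1 adds that "During each laboratory assessment, measurements will be performed to assess key cervical muscle attributes", and the schedule in Section 1.3 lists neck strength at all four assessments, so an assessor might try to guess an athlete's arm. What would be at stake is the credibility of the assessor blind and of the Time Point 4 comparison.

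**Working it through.** The question is mainly one of reading the sections together. One calculation shows how informative results by arm could be.

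**1. What the word can describe.** There are three candidates: the analyst, the first reader and the output. Section 6.2 rules out the first two, because the statistician and the PI are named as unblinded. Only the output is left. An unblinded statistician who produces masked or pooled output is ordinary practice and contradicts nothing.

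**2. What assessors would learn under each reading.**

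| Output released | Comparison of named arms shown? | Any athlete's allocation shown? |
|---|---|---|
| Pooled | No | No |
| Arms masked | No, though the direction may be guessed | No |
| Arms named, group averages | Yes | No |

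The third row does not fit the label in Section 9.4.5. In no row does an assessor learn an athlete's arm. Guessing from measured neck strength is possible at every visit with or without an interim.

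**3. What athletes would learn.** They already know which exercises they do. The expected direction is already in the protocol: Sections 9.2 and 9.4.2 both speak of a reduction in net head acceleration, with 20% as the working figure. (Section 9.1 states a dose-response effect but gives no direction.) Section 8.1 limits the scope for effort or expectation to act: loads are standardized, sEMG biofeedback checks muscle activation, three trials are averaged, and acceleration comes from a camera system. It also says results are not routinely given to participants, with individual requests left to the PI.

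**4. Effect on the final test.** The interim cannot halt study activities, so it creates no early-stopping opportunity to declare success. Section 9.4.1 sets alpha at .05, and no inflation from early stopping arises.

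**5. How informative results by arm could be.** Inputs from Section 9.2: 30 per group, standardized effect .6 to 1.0, slope multiplier 1.25. Alpha is .05 (Section 9.4.1); two-sided is assumed because the section does not say.

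Formula: power ≈ Φ(d√(n/2) − 1.96).

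- Plan's own figure: d = .6 × 1.25 = .75 and n = 30 give Φ(.75 × 3.873 − 1.96) = Φ(.945) = .83, as stated.
- Interim, lower effect: d = .75 and n = 15 give Φ(.75 × 2.739 − 1.96) = Φ(.094) = .54.
- Interim, upper effect: d = 1.0 × 1.25 = 1.25 and n = 15 give Φ(1.25 × 2.739 − 1.96) = Φ(1.463) = .93.

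Fifteen controls is an assumption, since Section 9.4.5 counts only the treatment group. Because the earlier trigger applies, the number of treatment completers is at most about 15. These figures show that results by arm, if released, could carry real information. They do not show that such results will be released, and they measure no bias.

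**The case for a change.** The strongest opposing case is that a label is not a rule. Preliminary results of a two-arm trial, triggered by a count in the treatment group, can fairly be read as comparative. Masking two arms may not hide much when the expected direction is written down. The DSMB already sees efficacy by arm and the interim has no stopping use, so nothing in the conduct of the trial needs comparative results outside the statistician and the DSMB. Pooled output now and comparative results after data lock would serve dissemination, at the price of later abstracts.

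Part of this stands. Section 9.4.5 does not spell out the limit, and one sentence would have done so. But the label is still limiting text, and it sits beside the standing blinding rule in Section 6.2. It would be too strong to say that nothing restricts the output. When to publish preliminary results is a choice the sponsor may make, and Section 9.4.5 ties the interim to the proposal funded by NIH. That proposal, the DSMB charter and the Manual of Procedures are not among the documents, and the section on key roles is absent from the public text. Any of these may define the term. The harm also needs a chain of steps: release by named arm, against the label; results reaching athletes or assessors; and a change in behaviour that survives standardized loading and biofeedback. The documents support none of these as planned.

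**Conclusion.** The gap is real but small, and no change to the plan follows. If the sponsor does what the word *blinded* says, the primary and secondary comparisons are as sound as they would be with a fuller definition. A longer sentence would record the meaning without altering any analysis, sample size or decision. Writing it in would take an amendment with IRB approval, and the start date is not given, so the interim may already have been done.

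No bias can be computed from the documents, no type I error inflation from early stopping arises, and no athlete's allocation is exposed by aggregate output. This rests on two assumptions: that the sponsor gives the word its ordinary meaning of output that does not compare identified arms, and that no unseen source says otherwise. Evidence that results by named arm were to be released before the last Time Point 4 assessment would reopen the question.
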